- c D1 pre-dose: Cycle 1 D1 refers to the day the participant receives the initial dose of IMP. D1 of Cycle 2 and of each subsequent cycle corresponds to D15 of the previous cycle. During treatment, D1 assessment can be done on the day of infusion (before infusion) or the day before. C1D1 hematology, blood chemistry, coagulation and urinalysis tests may be omitted if baseline test performed within 7 days are normal. If baseline tests are abnormal should be repeated within 2 days of first study intervention.
- d Follow-up visit: SAEs (regardless of relationship with study treatment) and IMP-related AEs ongoing at the end of study treatment, and any new IMP-related AE/SAE/AESI will be followed until resolution or stabilization (defined as an event ongoing without any change for at least 3 months). Date of disease progression and further anticancer treatment will be collected at the follow-up visit. Participants who stopped treatment before documented progressive disease (PD; ie, achieving stable disease [SD], or complete or partial response [CR or PR]) should undergo a tumor assessment and an on-site follow-up visit every 12 weeks (± 7 days) after the last tumor assessment until radiological disease progression, death, study cut-off date of the secondary ORR endpoint of the triplet cohort, initiation of further anti-cancer therapy, or withdrawal of participant's consent, whichever comes first. Participants with documented disease progression should attend an on-site follow-up visit 90 days after the last dose of study medication. If every ongoing related AE/SAE/AESI is resolved or stabilized, no further follow-up visit is needed.
- e Disease history includes previous antitumor therapy (type, start and end dates, reason for discontinuation and response to the therapy) and smoking history.
- f NSCLC characteristics will include histologic types, stage at diagnosis, disease extent at study entry, (collected at screening) and specific mutations including PD-1 expression status (to be collected only at prescreening).
- g Physical examination will include: vital signs (temperature, blood pressure, heart rate) and examination of major body systems. Signs and symptoms will be reported in the electronic case report form (eCRF) as AEs only if they are still present at the time of first IMP administration

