- h Hematology: Hemoglobin, hematocrit, RBC, WBC with differential, platelet counts. These tests will be done before IMP administration at each cycle. If Grade 4 neutropenia, assess absolute neutrophil count (ANC) every 2-3 days until ANC $\geq 0.5 \times 10^9/L$. During first 2 cycles, hematology will be performed weekly.
- i Coagulation: International normalized ratio (INR), aPTT.
- j Clinical blood chemistry: Liver function tests: SGOT (AST), SGPT (ALT), total bilirubin, conjugated bilirubin, AP. Renal function tests: Urea (or BUN) & creatinine. Electrolytes: Sodium, potassium, calcium, glucose. Others: LDH, albumin and total proteins. During first cycle, liver function tests will be performed weekly. The liver function tests and renal function tests will be done before IMP administration at each cycle, unless clinically appropriate. In case of Grade ≥ 3 liver function abnormal tests, additional tests will be repeated every 2-3 days until recovery to baseline value.
- k Urinalysis tests on morning spot will be performed by dipstick at baseline, and at every treatment cycle. In case of proteinuria $\geq ++$ (dipstick), proteinuria quantification by proteinuria/24 h should be performed.
- l Serum pregnancy test: women of childbearing potential must have a negative serum pregnancy test result within 7 days prior to the initial dose of IMP. A pregnancy test (serum/urine) will be repeated every 4 weeks before IMP administration, and a serum test will be repeated at the End of Treatment evaluation (30 \pm 5 days after the last IMP administration), and at the Follow-up visit (90 \pm 7 days after last IMP dose).
- m Echocardiogram or MUGA scan: left ventricular ejection fraction (LVEF) will be evaluated during screening period, and whenever clinically indicated.
- n 12-lead ECG is required at baseline (In case the ECG performed less than 7 days before 1st IMP administration is considered as normal, there is no need to repeat it just before the 1st IMP) before starting the and after completing the first IMP administration (within 30 minutes after the end of tusamitamab ravtansine infusion). The ECG after the infusion at cycle1 should be performed at any case; before IMP administration at each cycle; and at the End of treatment evaluation, 22 to 30 days after last IMP administration.

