3 OBJECTIVES AND ENDPOINTS

Table 3 - Objectives and endpoints

Doublet cohort

	Objectives	Endpoints
Primary		
	
Part 1 (safety run-in): To assess the tolerability and to confirm the recommended dose of tusamitamab ravidansine in combination with ramucirumab in the NSQ NSCLC populationPart 2: To assess the antitumor activity of tusamitamab ravidansine in combination with ramucirumab in the NSQ NSCLC population	
Part 1: Incidence of study drug-related dose-limiting toxicity (DLT) at Cycle 1 and Cycle 2 (C1D1 to C2D14). Anticipated DLT includes, but is not limited to, corneal toxicityPart 2: Objective response rate (ORR) defined as proportion of participants with confirmed complete response (CR) or partial response (PR) as best overall response (BOR) determined per Response Evaluation Criteria in Solid Tumors (RECIST) v1.1.
Secondary		

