Infusion of tusamitamab rfvansine will be administered at least 1 hour after the end of ramucirumab infusion. For patients with a BSA >2.20 m², the tusamitamab rfvansine dose will be calculated based on a BSA of 2.20 m².

The decision tree for doses in Part 1 is summarized in [Figure 4](#).

Figure 4 - Decision tree for the doublet cohort Part 1 for tusamitamab ravtansine

*Note: In case of 2 or more DLTs at DL -1, the cohort may be stopped or the dosage reconsidered.

Abbreviations: DL -1=dose level -1 (80 mg/m²); DLT=dose-limiting toxicity; RP2D=recommended dose.

Following the identification of the RP2D, Part 2 of the study will be initiated.

Dose limiting toxicity definition

All AEs specified in [Table 5](#) occurring during the first 2 cycles of treatment, unless due to disease progression or to a cause obviously unrelated to IMP, will be considered DLTs. The duration of the DLT observation period will be longer for a participant who delays initiation of Cycle 2 due to a treatment-related AE for which the event's duration would determine whether the AE meets the definition of a DLT. The NCI CTCAE version 5.0 will be used to assess the severity of AEs. Causal relationships are to be determined by the Investigator. The DLTs will be confirmed by the SC.

Table 5 - Dose-limiting toxicities

Hematological abnormalities
Grade 4 neutropenia for 7 or more consecutive days
Grade 3 to 4 neutropenia complicated by fever (temperature $\geq 38.5^{\circ}\text{C}$ on more than 1 occasion) or microbiologically or radiographically documented infection
Grade ≥ 3 thrombocytopenia associated with clinically significant bleeding requiring clinical intervention
Non-hematological abnormalities
Elevated urine protein ≥ 3 g/24 h
Grade 4 non-hematologic AE
Grade ≥ 3 keratopathy
Grade 4 or refractory hypertension
In addition, any other AE that the recruiting Investigators and Sponsor deem to be dose limiting, regardless of its grade, may also be considered as DLT.

Part 2: It is planned that 30 treated patients will be evaluable for response (the 6 patients from the safety run-in treated at the recommended dose will be included). During the treatment period, participants will have tumor assessments every 8 weeks.

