6.6.2 Triplet cohort

If ≥ 2 of the first 3 patients or of the 6 patients treated at the initial DL present with DLTs, the SC may decide to decrease the dose of tusamitamab rfvantsine to DL -1 (120 mg/m² in combination with 10 mg/kg ramucirumab). The tolerability of the reduced DL will be assessed in at least 6 participants. Dose reduction in the case of 2 or more DLTs for the cohort is shown in [Table 10](#).

Table 10 - Dose reduction for triplet cohort

Dose level (DL)	tusamitamab rfvantsine	ramucirumab	pembrolizumab
Starting dose	150 mg/m ² Q3W	10 mg/kg Q3W	200 mg Q3W
Minus -1 (DL-1)	120 mg/m ² Q3W	10 mg/kg Q3W	200 mg Q3W

DL=dose level; Q3W=every 3 weeks.

Infusion of tusamitamab rfvantsine will be administered at least 1 hour after the end of ramucirumab infusion. For patients with a BSA >2.20 m², the tusamitamab rfvantsine dose will be calculated based on a BSA of 2.20 m².

6.6.3 Doublet cohort (Part 1 and Part 2) and triplet cohort: Requirements for retreatment

For the retreatment of patients on Day 1 of each subsequent cycle, the following conditions should be met:

- Neutrophils count $\geq 1.5 \times 10^9/L$.
- Platelets $\geq 100 \times 10^9/L$.
- Total bilirubin $\leq 1.5 \times ULN$.
- AST, ALT $\leq 2.5 \times ULN$ or $\leq 5 \times ULN$ in case of documented liver metastasis.
- No IMP-related toxicity Grade >1 (except for alopecia) or baseline severity.
- Urine protein:
 - $<2+$ on dipstick or urinalysis for C1D1,
 - $\leq 2+$ on dipstick or urinalysis for subsequent infusions,
 - OR
 - <2 g on 24 hours urine collection.
- Hypertension is controlled, every attempt should be made to control blood pressure (<140 mmHg systolic and <90 mmHg diastolic).
- Wound healing: any wound is fully healed.

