8.2.5 Clinical safety laboratory assessments

See Appendix 2 ([Section 10.2](#)) for the list of clinical laboratory tests to be performed and to the SOA ([Section 1.3](#)) for the timing and frequency. In general, these tests will be done at each cycle; during the first 2 cycles, hematology and liver function tests will be assessed weekly.

If Grade 4 neutropenia occurs, assess ANC every 2 to 3 days until ANC $\geq 0.5 \times 10^9/L$.

In case of Grade ≥ 3 abnormal liver function tests, additional tests will be done every 2 to 3 days until recovery to the baseline value. Additional tests will be performed when clinically appropriate. This test can be performed before the study intervention administration on the same day or the day before.

The Investigator must review the laboratory reports and must document this review in the source documents.

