10.11.4 Study procedures

Depending on site status, if needed, Cycle 1 and Cycle 2 weekly safety laboratory assessment (hematology [differential WBC] and liver function tests [AST, ALT, total and direct bilirubin, ALP]) can be arranged to be performed either at a laboratory certified to perform these tests that is close to patient home, or via sampling at patient's home.

All efforts should be made to ensure that measurements of key parameters for efficacy endpoints can be performed at the site. If the Investigator is unable to guarantee that the protocol-required efficacy assessments can be conducted, no participant should be screened until the site confirms its capacity to perform the assessments.

As part of a site's contingency plan, a back-up site should be identified in advance in the case that the site delegated to perform the radiological tumor assessment is prevented from performing the

assessment by a regional or national emergency situation (eg, COVID-19 outbreak). The Investigator should ensure that the back-up site conducts the RECIST assessment in same manner as that used for baseline tumor assessments.

In the case that the primary tumor assessment site is incapacitated, ongoing patients would then be referred to the back-up site for tumor assessment. The Investigator/delegate should ensure the information on baseline assessment methods is shared with the back-up site's radiologist to ensure same method is followed for scans to be sent to IRC.

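### The doublet flow chart asks for weekly liver tests in Cycle 1 only, Section 8.2.5 asks for them in Cycles 1 and 2, and the dose-limiting toxicity window covers both cycles

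*Protocol*

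**What the plan says.** Two parts of the Protocol set the frequency of liver tests in the doublet cohort, and a third presupposes one.

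- **Section 1.3.1, footnote j:** "During first cycle, liver function tests will be performed weekly". After that, liver tests are due before dosing at each cycle. Repeats every 2-3 days start only once a Grade 3 or higher abnormality has been found.
- **Section 8.2.5:** "during the first 2 cycles, hematology and liver function tests will be assessed weekly". The sentence is not limited to either cohort.
- **Section 10.11.4 (emergency contingency):** speaks of "Cycle 1 and Cycle 2 weekly safety laboratory assessment" and includes the liver tests in it.

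Section 8.2.5 sends the reader to the schedule of activities for timing and frequency. The chemistry row of that schedule sends the reader back to Section 8.2.5.

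For hematology, footnote h of the same chart says "During first 2 cycles, hematology will be performed weekly".

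The Part 1 primary endpoint (Section 3, Table 3) is the incidence of study-drug-related DLTs from C1D1 to C2D14. Section 4.1, Table 5, has no liver-specific criterion. A liver-enzyme rise counts as a "Grade 4 non-hematologic AE", or if investigators and sponsor judge it dose limiting.

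**The concern.** A site that follows Section 8.2.5 meets both texts. A site that works from the flow chart alone meets only footnote j, and then no scheduled liver test looks at the effect of dose 2 before the DLT window closes.

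Hepatotoxicity is a listed potential risk of tusamitamab ravtansine (Section 2.3), and Section 8.2.6.5 reports enzyme increases with both drugs. Liver-enzyme rises can be symptom-free, so ascertainment depends on the blood draw. The run-in rule in Section 4.1 can turn on one participant: 1 DLT in 6 confirms the starting dose and 2 in 6 lowers it. What is at stake is whether the Cycle 1-2 DLT count was fully observed for liver events. Nothing in the documents shows that an event was missed.

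**Working it through.** **Inputs**

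- Cycle length 14 days; Day 1 of each cycle is D15 of the one before (1.3.1, footnote c).
- DLT window C1D1 to C2D14 (Section 3, Table 3), given as about 28 days in Section 4.1.
- Dosing window ±2 days (6.6.4).
- Footnote c: "During treatment, D1 assessment can be done on the day of infusion (before infusion) or the day before".

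**The plan's own figure.** 2 cycles × 14 days = 28 days. So C2D14 is study Day 28, and C3D1 is Day 29. The stated window length is reproduced.

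**Nominal liver tests**

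| Study day | Cycle day | Footnote j | Section 8.2.5 |
|---|---|---|---|
| 1 | C1D1, before dose 1 | yes* | yes* |
| 8 | C1D8 | yes | yes |
| 15 | C2D1, before dose 2 | yes | yes |
| 22 | C2D8 | no | yes |
| 29 | C3D1, before dose 3 | yes | yes |

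*Footnote c lets this one be omitted if the tests in the previous 7 days were normal.

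- Tests after dose 2 and by Day 28: 0 under footnote j, 1 (Day 22) under Section 8.2.5.
- Longest gap from Day 15 to Day 29: 29 − 15 = 14 days under footnote j; 22 − 15 = 29 − 22 = 7 days under Section 8.2.5.

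**Can the Cycle 3 pre-dose test fall inside the window?** Dose 3 may be given 14 ± 2 days after C2D1, that is 12 to 16 days later, on C2D13 to C2D17.

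- Drawn the same day: C2D13 and 14 are inside; C2D15, 16 and 17 are outside (2 of 5 inside).
- Drawn the day before: C2D12, 13 and 14 are inside; C2D15 and 16 are outside (3 of 5 inside).

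So 5 of the 10 allowed timings are inside. This is a plain count, not a probability. A test can fall in the window, but none is required there, and the nominal same-day draw on C2D15 is one day late.

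**Which text is out of line?**

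| Weekly schedule in the flow charts | Cycles | DLT window (cycles) |
|---|---|---|
| Doublet hematology (1.3.1, h) | 2 | 2 |
| Doublet liver (1.3.1, j) | 1 | 2 |
| Triplet hematology (1.3.2, h) | 1 | 1 |
| Triplet liver (1.3.2, j) | 1 | 1 |

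Three of the four match their DLT window. Doublet liver testing is the exception.

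**Has Part 1 finished?** The SAP version history gives first enrolment as 28-Oct-2020 and amended protocol 02 as 20 December 2022: 730 days to 28-Oct-2022, plus 53, makes 783 days. That amendment bases the triplet dose on doublet experience (Protocol 4.3) and uses doublet failure rates (9.2). Part 1 has very likely finished, though no text says so outright.

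**The case against.** The strongest reply is that the Protocol, read as a whole, already requires the Day 22 test. Footnote j does not exclude testing in Cycle 2, Section 8.2.5 asks for it in plain words, and the flow chart points there. On that reading this is unharmonised wording and nobody chose a 14-day gap. That is fair, and it is the main reason the point is small. It does not remove the conflict, because Section 8.2.5 hands timing and frequency back to the flow chart. Section 10.11.4 adds only indirect support, since it presupposes a schedule and does not set one.

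The second reply is that little would be lost, and most of this stands. A rise still present before dose 3 would be seen at the retreatment check (6.6.3). Grade 4 AST/ALT increases are serious adverse events (10.2, Table 18 note a), and liver-enzyme increases of Grade 3 or higher are of special interest (8.3.1). The Study Committee reviews the data during Part 1 (10.1.5). Protocol 9.4.2.1 does not settle how to class an event found on Day 29 that blocks dose 3, because no later cycle has then begun. SAP Table 10, however, collects events entered on the DLT page outside the observation period. What escapes all of this is a symptom-free Grade 4 rise that appears after dose 2 and resolves before the next draw. The documents give no rate for that.

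Third, editing the footnote cannot change a Part 1 count that has probably closed. That is right for the footnote edit.

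Fourth, the triplet footnotes also say one cycle and so differ from Section 8.2.5, which names no cohort. This is true and remains after the change proposed here. The triplet DLT window is Cycle 1 only, so that mismatch leaves no hole in its primary endpoint.

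**Conclusion.** The concern holds, as a minor point. The two texts disagree. Under the flow chart alone, no liver test is required between dose 2 and C2D14, against one under Section 8.2.5. For the DLT endpoint this touches the 6 to 12 DLT-evaluable participants expected in Part 1 (9.2.1).

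The weakness is in the completeness of the Cycle 1-2 count: a transient symptom-free Grade 4 rise could be missed, and one first found on Day 29 could fall outside the strict window. An event that is found is not lost to reporting or to the Study Committee.

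The day count assumes nominal dosing every 14 days and no extra clinically driven tests. How many sites followed which text cannot be told from the documents.

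**What to change.** In Protocol 1.3.1, footnote j, change the weekly liver-test sentence from the first cycle to the first 2 cycles, to agree with Section 8.2.5 and footnote h. The added panel goes on the existing Day 22 hematology draw. Leave Sections 8.2.5, 8.2.6.3 and 10.11.4 as they are, and remove no triplet monitoring.

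As an optional addition, because Part 1 has probably finished, report how many DLT-evaluable Part 1 participants had at least one liver test after dose 2 and by C2D14. The SAP (4.7.3.1) already uses scheduled, unscheduled and repeat laboratory values, and the final analysis in SAP 4.9 is a natural place for the count.

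The cost is one phrase and, if the count is added, a tally over 6 to 12 people from dates already held. Extra panels number 0 for anyone already past C2D8, and at most about 36 (one for each planned treated doublet participant) if nobody had reached it. The documents do not give the enrolment status that would fix the number.

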1.3.2 Study flow chart - Triplet cohort

Procedure	Pre-screening ^a	Screening ^b	Treatment cycle 1		Treatment cycle 2 +		End of treatment	90 (± 7) Days (3 month) Follow-up ^d	Notes*
Day		Days to first infusion	D1		21 (± 3) days from previous infusion		30 (± 5) days from last infusion		
			Pre-infusion ^c	EOI	Pre-infusion ^c	Every 6 weeks (± 7 days)			
CEACAM5 expression status ^a (archival or fresh tumor tissue) – central IHC/ prescreening Informed consent	X								
Informed Consent		X							
Inclusion/exclusion criteria		≤ 28	X						Section 5.1, 5.2
Demography, medical/surgical/disease/smoking history ^e		≤ 28							
NSCLC characteristics ^f	X	≤ 28							
Height		≤ 7							
Performance status (ECOG)		≤ 7	X		X		X	X	Section 8.2.1, 8.2.3
Physical examination, including vital signs, body weight ^g		≤ 7	X		X		X	X	Section 8.2.1
Hematology ^h		≤ 7	X		X		X		Section 8.2.5, 10.2 (Appendix 2)
Coagulation ⁱ		≤ 7	X		X		X		Section 10.2 , (Appendix 2)
Clinical blood chemistry ^j		≤ 7	X		X		X		Section 8.2.5, 10.2 (Appendix 2)
Thyroid function		≤ 7			X		X		
Urinalysis ^k		≤ 7	X		X				Section 10.2 , (Appendix 2)
HBsAg & HCV serology and HIV test (only if required at country level)		X							Section 10.8 , (Appendix 8)

Procedure	Pre-screening ^a	Screening ^b	Treatment cycle 1		Treatment cycle 2 +		End of treatment	90 (± 7) Days (3 month) Follow-up ^d	Notes*
Day		Days to first infusion	D1		21 (± 3) days from previous infusion		30 (± 5) days from last infusion		
			Pre-infusion ^c	EOI	Pre-infusion ^c	Every 6 weeks (± 7 days)			
Urine or Serum pregnancy test ^l		≤ 7			X		X	X	Section 10.2 (Appendix 2) Section 10.5 (Appendix 5)
Left ventricular ejection fraction (MUGA/echocardiogram) ^m		≤ 28							Section 8.2.4.2
12-lead ECG ⁿ		≤ 7	X	X	X		X		Section 8.2.4.1
Specific ocular tests ^o		≤ 28					X		Section 8.2.2
Tusamitamab ravtansine/Ramucirumab/Pembrolizumab administration			X		X				Section 6.1
AE assessment ^p	X		Continuously throughout the study period						Section 8.2, 8.3, 10.3 (Appendix 3)
Concomitant medication ^q		X	Continuously throughout the study period						Section 6.5
Tumor assessment – RECIST v1.1 - CT/MRI; relevant surrogate markers ^r		≤ 28				X	X	X	Section 8.1
Circulating CEA ^s	X	≤ 28				X	X	X	
IgG			X						
Record further anticancer therapy								X	
Tusamitamab ravtansine PK			Refer to PK/ATA flowchart, Section 1.3.3						Section 8.5
Tusamitamab ravtansine Immunogenicity			Refer to PK/ATA flowchart, Section 1.3.3						Section 8.9

Abbreviations: AE=adverse event; AESI=AE of special interest; ALT (SGPT)=alanine aminotransferase; AST (SGOT)=aspartate aminotransferase; ATA=antitherapeutic antibody; CEA=carcinoembryonic antigen; CEACAM5=carcinoembryonic antigen-related cell adhesion molecule 5; CR=complete remission; CT=computed tomography; eCRF=electronic case report form; ECOG=Eastern Cooperative Oncology Group (performance status); ECG=electrocardiogram; EOI=end of infusion; HBsAg=hepatitis B virus surface antigen; HCV=hepatitis C virus; HIV=human immunodeficiency virus; IMP=investigational medicinal product; LVEF=left ventricular ejection fraction; MRI=magnetic resonance imaging; MUGA=multigated acquisition scan; NSCLC=non-small-cell lung cancer; PD=progressive disease; PK=pharmacokinetic; PR=partial response; RBC=red blood cells; RECIST=Response Evaluation Criteria in Solid Tumors; SAE=serious AE; SD=stable disease; WBC=white blood cells.

- a Prescreening: a prescreening-Informed Consent will be signed by the patient for CEACAM5 assay on archival or fresh tumor tissue and circulating CEA assay unless results are available from an assay for circulating CEA and from CEACAM5 testing for another study; in this case, an addendum to the informed consent will be sufficient.
- b Screening: Informed consent should be signed before any study specific procedures. It can be signed more than 28 days prior to initiation of therapy. Screening time indicates in which timeframe exams used to support eligibility have to be done prior to initiation of therapy. All the tests or procedures on D1 should be done at predose time unless otherwise stated. Assessments must be performed prior to first IMP administration: participants must have confirmed CEACAM5 expression as assessed centrally. Baseline evaluation should be completed within 1 week prior to initiation of therapy, except for tumor assessment, circulating CEA, echocardiography, and ocular tests that may be performed within 4 weeks prior to the first IMP administration. Results of these tests should be reviewed by the Investigator prior to initiation of therapy.
- c D1 pre-dose: Cycle 1 D1 refers to the day the participant receives the initial dose of IMP. D1 of Cycle 2 and of each subsequent cycle corresponds to D22 of the previous cycle. During treatment, D1 assessment can be done on the day of infusion (before infusion) or the day before. C1D1 hematology, blood chemistry, coagulation and urinalysis tests may be omitted if baseline test performed within 7 days are normal. If baseline tests are abnormal should be repeated within 2 days of first study intervention.
- d Follow-up visit: SAEs (regardless of relationship with study treatment) and IMP-related AEs ongoing at the end of study treatment, and any new IMP-related AE/SAE/AESI will be followed until resolution or stabilization (defined as an event ongoing without any change for at least 3 months). Date of disease progression and further anticancer treatment will be collected at the follow-up visit. Participants with documented disease progression should attend an on-site follow-up visit 90 days after the last dose of study medication. If every ongoing related AE/SAE/AESI is resolved or stabilized, no further follow-up visit is needed.
- e Disease history includes previous antitumor therapy (type, start and end dates, reason for discontinuation and response to the therapy) and smoking history.
- f NSCLC characteristics will include histologic types, stage at diagnosis, disease extent at study entry, (collected at screening) and specific mutations including PD-1 expression status (to be collected only at prescreening).
- g Physical examination will include: vital signs (temperature, blood pressure, heart rate) and examination of major body systems. Signs and symptoms will be reported in the electronic case report form (eCRF) as AEs only if they are still present at the time of first IMP administration
- h Hematology: Hemoglobin, hematocrit, RBC, WBC with differential, platelet counts. These tests will be done before IMP administration at each cycle. If Grade 4 neutropenia, assess absolute neutrophil count (ANC) every 2-3 days until ANC $\geq 0.5 \times 10^9/L$. During first cycle, hematology will be performed weekly.
- i Coagulation: International normalized ratio (INR), aPTT.
- j Clinical blood chemistry: Liver function tests: SGOT (AST), SGPT (ALT), total bilirubin, conjugated bilirubin, AP. Renal function tests: Urea (or BUN) & creatinine. Electrolytes: Sodium, potassium, calcium, glucose. Others: LDH, albumin and total proteins. During first cycle, liver function tests will be performed weekly. The liver function tests and renal function tests will be done before IMP administration at each cycle, unless clinically appropriate. In case of Grade ≥ 3 liver function abnormal tests, additional tests will be repeated every 2-3 days until recovery to baseline value.
- k Urinalysis tests on morning spot will be performed by dipstick at baseline, and at every treatment cycle. In case of proteinuria $\geq ++$ (dipstick), proteinuria quantification by proteinuria/24 h should be performed.
- l Serum pregnancy test: women of childbearing potential must have a negative serum pregnancy test result within 7 days prior to the initial dose of IMP. A pregnancy test (serum/urine) will be repeated every 4 weeks before IMP administration, and a serum test will be repeated at the End of Treatment evaluation (30 \pm 5 days after the last IMP administration), and at the Follow-up visit (90 \pm 7 days after last IMP dose).
- m Echocardiogram or MUGA scan: left ventricular ejection fraction (LVEF) will be evaluated during screening period, and whenever clinically indicated.
- n 12-lead ECG is required at baseline (In case the ECG performed less than 7 days before 1st IMP administration is considered as normal, there is no need to repeat it just before the 1st IMP) before starting and after completing the first IMP administration (within 30 minutes after the end of tusamitamab ravtansine infusion); before IMP administration at each cycle; and at the End of treatment evaluation, 22 to 30 days after last IMP administration.
- o Specific ocular tests will include assessment of ocular/visual symptoms and ocular exams including visual acuity, slit lamp under dilatation, and Schirmer's test at screening and whenever clinically indicated.
- p AE: For participant who was prescreened and had fresh biopsy, only the Adverse Events related to the fresh biopsy procedure itself should also be reported in eCRF as general requirement of AE/SAE with the reporting time frame interval of 1 month for the prescreening period after fresh biopsy.
- q Concomitant medication will be recorded in the eCRF from 28 days prior to the first study intervention administration, before every cycle during the study treatment period, and for up to 30 days after the final dose of study intervention. Once the participant has withdrawn from study treatment, concomitant medication should only be recorded if used to treat new or unresolved study treatment-related adverse events.
- r Tumor assessment will be made at every 6 weeks interval (± 7 days window) during the study treatment period until radiological disease progression; initiation of further anti-cancer therapy; death; or study cut-off of the secondary ORR endpoint of the triplet cohort. The scheduled tumor assessment time point will not be modified in case of a cycle delay.
- s CEA samples should be collected before IMP infusion.

